5.2.3.3. Case Accrual Plot

The plot for the estimated cumulative number of cases/attack rate/incidence rate of first laboratory-confirmed influenza, caused by any influenza viral types/subtypes, associated with the occurrence of a protocol-defined ILI over time (days since vaccination), by study intervention, for each group (18 through 64 years of age, ≥ 65 years of age), separately, will be produced.

5.3. Methods to Manage Missing Data

5.3.1. Safety Data

Standard algorithms for handling missing AE dates, missing AE severity levels, missing laboratory test values, and missing ECG values will be applied according to the Pfizer safety rules. Missing data handling rules on the safety data are described in detail in the corresponding endpoint sections.

5.3.1.1. Reactogenicity Data

Completely missing reactogenicity e-diary data will not be imputed.

For derived variables based on reactogenicity data, if data for any day of the 7-day e-diary are available, the “any day (Day 1 through 7)” data will be considered nonmissing.

The reactogenicity data are collected through the reactogenicity e-diary, which does not allow participants to skip a question. Therefore, for a specific day, if the e-diary data are transferred for that day, all the reactogenicity data for the participant on that day are nonmissing. No missing reactogenicity data will be imputed other than what is described in [Section 3.1.2.1](#) and [Section 3.1.2.2](#).

In summary, for any participant with all 7 days of the e-diary missing, this will not be included in the analysis (ie, assuming MCAR). If only 1 to 6 days of e-diary data are transferred, the reactogenicity data for the missing day(s) are considered as answering “no” for all reactions. This is based on the common assumption that no reports mean no events.

5.3.2. Immunogenicity Data

Any assay results above the LLOQ are considered accurate, and their quantitated values will be reported. Antibody titers below the LLOQ, denoted as BLQ, or below the LOD will be set to **CCI** for GMT analysis. If the LLOQ is missing and the LOD is available for either serum or **CCI** data, the LOD will be used for LLOQ.

No other missing assay data will be imputed in the analyses. All immunogenicity analyses will be performed after the imputation of the antibody concentrations or antibody titers that are below the LLOQ.

When calculating a fold rise, the assay results will be converted to **CCI** if assay results are < LLOQ, except when the prevaccination assay result is < LLOQ while the postvaccination result is \geq LLOQ, in which case the prevaccination value will be set to the LLOQ. If both the numerator and denominator are < LLOQ, then both will be converted in the same way.

Values for sera that are insufficient (QNS), indeterminate results, or values recorded as “not done” will be set to “missing.” Additionally, any time point with no blood draws will not be included in the analysis. No imputation will be done for these missing values, as MCAR is assumed for immunogenicity data.

LLOQ results for each assay used in this study will be included in serology data transfer once they are available.

5.3.3. Efficacy Data

Participants who discontinued from the study because of either loss to follow-up or death will be assumed to have no cases after the discontinuation for the analysis of efficacy-related endpoints.

Missing laboratory results such as “indeterminate,” “QNS,” or “not done” from the PCR test will be considered **CCI** when used to determine **CCI**. This approach will decrease the sensitivity of case detection and would only underestimate the VE. No other sensitivity analysis is planned.

6. ANALYSES AND SUMMARIES

6.1. Primary Endpoint(s)

6.1.1. First-Episode LCI Cases With Associated Per-Protocol ILI in Participants 18 Through 64 Years of Age and in Participants ≥ 65 Years of Age

6.1.1.1. Main Analysis

- Estimand strategy: Hypothetical approach ([Section 2.2.1](#)).
- Analysis set: Evaluable efficacy population ([Section 4](#)).
- Analysis timing: At the time of sufficient case accrual in either age group or final analysis when the influenza season ends.
- Analysis methodology: RVE is calculated with 1 - risk ratio and will be expressed as a percentage. The risk ratio is the total number of first-episode LCI cases in the qIRV group compared to that in the QIV group. The CI of the RVE will use the conditional exact test based on the binomial distribution of the number of cases in the qIRV group, given the total number of cases in both groups, as specified in [Section 5.2.3.1](#).
- Intercurrent events and missing data: Data collected after an intercurrent event will not be included. Missing data will not be imputed ([Section 5.3.3](#)).
- Reporting results:
 - The sample size, total number of first-episode LCI cases, and proportion of participants with LCI cases will be presented for each study intervention by age group (18 through 64 years of age, ≥ 65 years of age).
 - The estimated RVE and 95% CI for the VE using the exact method will be presented ([Section 5.2.3.1](#)).
 - A case accrual curve will be plotted by age group (18 through 64 years of age, ≥ 65 years of age).
 - RVE over time (by Months 1, 2, 3, etc, after vaccination) will be plotted by age group.

6.1.1.2. Sensitivity/Supplementary Analysis

To support the assessment of RVE, an analysis of the primary efficacy endpoint will be performed by adjusting for person-time through the Poisson regression and Cox regression⁵ models [Section 5.2.3.2](#). An additional analysis of the primary efficacy endpoint using a treatment policy estimand strategy will be performed by age group. It will use the same methodology and summary as the main analysis, but observations that occur after the intercurrent events of study withdrawal or important protocol deviation will be included.

6.1.2. Local Reactions and Systemic Events

6.1.2.1. Main Analysis

- Estimand strategy: Treatment policy ([Section 2.2.1](#)).
- Analysis set: Reactogenicity e-diary safety population ([Section 4](#)).
- Analysis methodology: 95% CI of the proportion of participants reporting each event, using the Clopper-Pearson method ([Section 5.2.1](#)).
- Intercurrent events and missing data: The participants without any e-diary data throughout the 7 days after vaccination will be excluded from the analysis at that vaccination; for participants who discontinue, all collected data will be included; intermediate missing values will not be imputed. Partially missing e-diary data are imputed as “no” ([Section 5.3.1.1](#)); e-diary data that are confirmed as errors will not be used for analysis.
- Analysis timing: Day 1 through Day 7 after vaccination.
- Reporting results:
 - Descriptive statistics, including the proportion (%), the numerator (n) and the denominator (N) used in the proportion calculation, and the 95% CI for percentage using the Clopper-Pearson method, will be presented, by each study intervention group, for each age group (18 through 64 years of age, ≥ 65 years of age).
 - Bar charts with the proportions of participants for each and any local reaction, and each and any systemic event, through the 7 days following vaccination will be plotted, by each study intervention group, for each age group (18 through 64 years of age, ≥ 65 years of age). The bars will be divided into severity categories to highlight the proportions of participants by maximum severity.

6.1.2.2. Sensitivity/Supplementary Analyses

To support the assessment of reactogenicity, the endpoints below, as specified in [Section 3.1.2.1](#) and [Section 3.1.2.2](#), will be summarized with the same analysis time point and analysis population:

- Duration (days) of each local reaction and each systemic event after vaccination.
- Onset day of each local reaction and each systemic event after vaccination.

The presentation of the results will include a basic descriptive summary without 95% CIs ([Section 5.2.1](#)).

These continuous endpoints will be summarized by displaying the n, mean, median, standard deviation, minimum, and maximum for each study intervention group by each age group (18 through 64 years of age, ≥ 65 years of age).

In addition, the proportions of participants reporting prompted local reactions and systemic events by maximum severity level with any e-diary errors will be included as a supplemental summary.

6.1.3. AEs and SAEs

6.1.3.1. Main Analysis

- Estimand strategy: Treatment policy ([Section 2.2.1](#)).
- Analysis set: Safety population ([Section 4](#)).
- Analysis methodology: 95% CI of the proportion of participants reporting those events, using the Clopper-Pearson method ([Section 5.2.1](#)).
- Analysis timing: Day 1 through 4 weeks after vaccination for AEs; Day 1 through 6 months after vaccination for SAEs.
- Intercurrent events and missing data: All data collected are included. Missing AE dates will be imputed as described in Pfizer's Vaccine Statistics Rulebook.
- Reporting results:
 - The number of participants with AEs through 4 weeks after vaccination (n), proportion (%), and associated 2-sided Clopper-Pearson 95% CI, will be presented by each study intervention group, separately, for each analysis interval ([Section 3.1.2.4](#)), and for each age group (18 through 64 years of age, ≥ 65 years of age), and overall.
 - The number of participants with SAEs through 6 months after vaccination (n), proportion (%), and associated 2-sided Clopper-Pearson 95% CI will be presented by each study intervention group, separately, for each analysis interval ([Section 3.1.2.5](#)), and for each age group (18 through 64 years of age, ≥ 65 years of age), and overall.
 - Descriptive statistics, including the proportion (%), the numerator (n) and the denominator used in the proportion calculation, and the 95% CI for percentage using the Clopper-Pearson method, will be presented, by each SOC and PT within each SOC, by study intervention group for each age group (18 through 64 years of age, ≥ 65 years of age), and overall.

6.1.3.2. Sensitivity/Supplementary Analysis

To support the assessment of AEs, the endpoints below as specified in [Section 3.1.2.4](#) and [Section 3.1.2.5](#) will be summarized with the same analysis population using the same presentation as specified in the main analysis:

- Immediate AEs;
- Related AEs;
- Severe AEs;
- Life-threatening AEs;
- AEs leading to study withdrawal;
- AEs leading to death;
- AESIs.

All AEs/SAEs after informed consent and prior to vaccination will not be included in the analyses but will be listed.

In addition, any AEs occurring up to 48 hours after blood draws or collection of midturbinate swabs will be listed separately.

6.2. Secondary Endpoint(s)

6.2.1. Immunogenicity Measured by HAI Titers

6.2.1.1. Main Analysis

The antibody titers measured by HAI assays [CCI](#) [CCI](#) will be analyzed separately. The analysis of antibody titers based on the HAI assay [CCI](#) [CCI](#) will have the following attributes. The analysis of the antibody titers based on the HAI assay [CCI](#) [CCI](#) will have the same attributes but will be based on the evaluable immunogenicity population (HAI assays [CCI](#) [CCI](#)).

- Estimand strategy: Hypothetical approach ([Section 2.2.3](#)).
- Analysis set: Evaluable immunogenicity population (HAI assays [CCI](#) [CCI](#)) ([Section 4](#)).
- Analysis methodology: Calculation of GMR and difference in seroconversion, as well as descriptive summary statistics ([Section 5.2.1](#) and [Section 5.2.2](#)).
- Analysis timing: Day 1, 4 weeks after study intervention.

- Intercurrent events and missing data: All data collected after or at intercurrent events will be excluded. Antibody titers data will be handled as described in [Section 5.3.2](#). Missing data will not be imputed.
- Reporting results:
 - GMRs for each strain in qIRV recipients compared to QIV recipients, and associated 2-sided 95% CIs, will be presented 4 weeks after study intervention, separately, for each age group (18 through 64 years of age, ≥ 65 years of age) in the northern hemisphere.
 - The difference in percentage of participants achieving seroconversion for each strain 4 weeks after vaccination in qIRV recipients compared to QIV recipients, and associated 2-sided 95% CIs, will be provided, separately, by age group (18 through 64 years of age, ≥ 65 years of age) in the northern hemisphere.
 - Descriptive statistics, including the sample size (n), GMTs, GMFRs, and 95% CI for the GMTs and GMFRs, will be presented, by study intervention ([Section 5.2.2](#)) and strain, separately, for each age group in the northern hemisphere and southern hemisphere, respectively.
 - The proportion of participants with HAI titers $\geq 1:40$ for each strain before vaccination and at each time point after vaccination, and the associated 2-sided Clopper-Pearson 95% CIs, will be provided, by study intervention, separately, for each age group (18 through 64 years of age, ≥ 65 years of age) in the northern hemisphere and southern hemisphere, respectively.
 - Empirical RCDCs will be plotted, by study intervention, separately, for each age group (18 through 64 years of age, ≥ 65 years of age) in the northern hemisphere and southern hemisphere, respectively.
 - The proportion of participants achieving HAI seroconversion 4 weeks after study intervention for each strain, and the associated 95% CIs, will be provided, by study intervention, separately, for each age group (18 through 64 years of age, ≥ 65 years of age) in the northern hemisphere and southern hemisphere, respectively.
 - The pooled immunogenicity analysis (eg, GMT, GMFR, proportion of participants with HAI titers $\geq 1:40$, proportion of participants achieving HAI seroconversion) may be done for each common strain in both northern hemisphere and southern hemisphere influenza seasons.

6.2.1.2. Sensitivity/Supplementary Analysis

To support the assessment of immunogenicity estimands, as specified in [Section 2.2.2](#), the treatment policy strategy might be summarized with the mITT immunogenicity populations using the same presentation as specified in the main analysis.

6.2.2. First-Episode CCI or LCI Cases With Different Definitions of ILI

All or selected analyses and data presentation for the primary endpoint ([Section 6.1.1](#)) will be repeated for following secondary efficacy endpoints by each group (18 through 64 years of age and ≥ 65 years of age), separately.

- First-episode LCI cases with associated per-protocol ILI, caused by all matched strains.
- First-episode LCI cases with associated per-protocol ILI, caused by each matched strain.
- First-episode LCI cases with associated per-protocol ILI, caused by unmatched strains.
- First-episode CCI cases with associated per-protocol ILI, caused by any strain.
- First-episode LCI associated with ILI, as defined by applying a modified CDC definition, caused by any strain.
- First-episode LCI cases associated with ILI, as defined by applying the WHO definition, caused by any strain.
- First-episode cases of influenza, as confirmed by central or local RT-PCR or culture, with associated per-protocol ILI.

6.3. Other/Exploratory Endpoint(s)

CC1

1

1

1

1

1

1

1

1

1

1

1

1

1

1

1

1

[figure not shown]
1

1

1

1

1

6.4. Subset Analyses

Selected efficacy endpoints, immunogenicity endpoints, local reactions, systemic events, and AEs/SAEs will be analyzed by the following categories:

- Age group (18-49 years of age, 50-64 years of age, 65-74 years of age, 75 years of age or older),
- Sex,
- Race,
- Ethnicity, and
- Influenza virus type.

6.5. Baseline and Other Summaries and Analyses

6.5.1. Baseline Summaries

6.5.1.1. Demographic Characteristics and Medical History

Descriptive summary statistics for demographic characteristics (age at vaccination, sex, race, ethnicity, and racial designation) will be generated, by study intervention, for each age group (18 through 64 years of age, ≥ 65 years of age) and for all participants in total, based on the safety population.

Each reported medical history term will be mapped to a SOC and PT according to MedDRA. The number and percentage of participants with an assigned vaccine having at least 1 diagnosis, overall and at each SOC and PT level, will be summarized by study intervention and for all participants in total, based on the safety population.

6.5.2. Study Conduct and Participant Disposition

6.5.2.1. Participant Disposition

All randomized participants will be included in the disposition summaries. Summaries will be displayed by study intervention, separately, for each age group (18 through 64 years of age, ≥ 65 years of age).

The number and percentage of randomized participants will be included in the participant disposition summary. In addition, the number and percentage of participants who received vaccinations, completed the follow-up visits, and withdrew before each follow-up visit phase, along with the reasons for withdrawal, will be tabulated by study intervention group and the total sample for each age group (18 through 64 years of age, ≥ 65 years of age). The reasons for withdrawal will be those as specified in the database.

Participants excluded from each analysis population will also be summarized, separately, by study intervention group, along with the reasons for exclusion by study intervention for each age group (18 through 64 years of age, ≥ 65 years of age).

A listing of protocol deviations may also be provided.

6.5.2.2. Blood Samples for Assay

For each blood sampling time point, the number and percentage of randomized participants providing blood samples within the protocol-specified time frame, as well as before and after the specified protocol-specified time frame, will be tabulated, separately, by study intervention for each age group (18 through 64 years of age, ≥ 65 years of age).

6.5.2.3. E-Diaries

The participants who were vaccinated and who transmitted and completed their e-diaries, as defined in [Section 3.4.2](#), will be summarized according to the vaccine received for each age group (18 to 64 years of age, ≥ 65 years of age). The summary will also include the number and percentage of vaccinated participants not transmitting the e-diary, transmitting the e-diary, and completing the e-diary for any day in the required reporting period, by assigned study intervention, for each age group.

The number and percentage of participants transmitting and completing the e-diary for each day and all days (Day 1 to Day 7) in the required reporting period will be tabulated for each study intervention, by each age group (18 through 64 years of age, ≥ 65 years of age).

The reactogenicity e-diary safety population will be used.

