## 9.2. Analysis Sets

For purposes of analysis, the following analysis sets are defined:

Population	Description
Screened	All participants who sign the ICD.
Randomized	All participants who are assigned a randomization number in the IRT system.
Evaluable immunogenicity (HAIs CCI [REDACTED])	All participants included in the immunogenicity subset who are eligible, receive the study intervention to which they were randomized, have blood drawn for assay testing within the specified time frame after vaccination, have at least 1 valid and determinate assay result (HAIs CCI [REDACTED]) at the 4-week postvaccination visit, and have no major protocol violations.
Evaluable immunogenicity (HAIs CCI [REDACTED])	All participants included in the immunogenicity subset who are eligible, receive the study intervention to which they were randomized, have blood drawn for assay testing within the specified time frame after vaccination, have at least 1 valid and determinate assay result (HAIs CCI [REDACTED]) at the 4-week postvaccination visit, and have no major protocol violations.
mITT immunogenicity (HAIs CCI [REDACTED])	All randomized participants in the immunogenicity subset who receive the study intervention and have at least 1 valid and determinate assay result (HAIs CCI [REDACTED]) after vaccination.
mITT immunogenicity (HAIs CCI [REDACTED])	All randomized participants in the immunogenicity subset who receive the study intervention and have at least 1 valid and determinate assay result (HAIs CCI [REDACTED]) after vaccination.
Evaluable efficacy	All participants who are eligible, receive the study intervention to which they were randomized, and have no major protocol violations before the symptom onset date of the confirmed LCI case, starting at least 14 days after vaccination, and associated with a per-protocol ILI.

Population	Description
mITT efficacy	All randomized participants who receive the study intervention.
Safety	All participants who receive the study intervention.
Reactogenicity e-diary safety	All participants who receive the study intervention and have at least 1 day of e-diary transferred for reactogenicity.

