3.4.2. E-Diary Completion

An e-diary will be considered transmitted if any data for the 3 local reactions (redness, swelling, pain at the injection site), 7 systemic events (vomiting, diarrhea, headache, fatigue, chills, new or worsening muscle pain, and new or worsening joint pain) and fever, or use of antipyretic/pain medication to treat symptoms, are present on any day. If all data are missing for all items on the e-diary for all 7 days after vaccination, then the e-diary will be considered not transmitted.

An e-diary will be considered completed if all expected data for all 7 days are available (ie, not missing). Otherwise, the e-diary will be considered incomplete. For any given day, an e-diary will be considered complete if all expected data are available.

For transmitted e-diaries, the following variables will be defined: “Day 1,” “Day 2,” “Day 3,” “Day 4,” “Day 5,” “Day 6,” and “Day 7.”

For completed e-diaries, the following variables will be defined: “Day 1,” “Day 2,” “Day 3,” “Day 4,” “Day 5,” “Day 6,” “Day 7,” and “Day 1 through Day 7.”

“Day 1-Day 7” is the variable for participants who completed e-diaries on all 7 days.

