4. ANALYSIS SETS (POPULATIONS FOR ANALYSIS)

Data for all participants will be assessed to determine if participants meet the criteria for inclusion in each analysis population prior to unblinding and releasing the database, and classifications will be documented per standard operating procedures.

Population	Description
Screened	All participants who sign the ICD.
Randomized	All participants who are assigned a randomization number in the IWRS.
Evaluable immunogenicity (HAI assays CCI [REDACTED])	All participants included in the immunogenicity subset who are eligible, receive the study intervention to which they were randomized, have blood drawn for assay testing within the specified time frame (CCI [REDACTED]), have at least 1 valid and determinate assay result (HAI assays CCI [REDACTED]) at the 4-week postvaccination visit, and have no important protocol deviations.
Evaluable immunogenicity (HAI assays CCI [REDACTED])	All participants included in the immunogenicity subset who are eligible, receive the study intervention to which they were randomized, have blood drawn for assay testing within the specified time frame (CCI [REDACTED]), have at least 1 valid and determinate assay result (HAI assays CCI [REDACTED]) at the 4-week postvaccination visit, and have no important protocol deviations.
mITT immunogenicity (HAI assays CCI [REDACTED])	All randomized participants in the immunogenicity subset who receive the study intervention and have at least 1 valid and determinate assay result (HAI assays CCI [REDACTED]) after vaccination.
mITT immunogenicity (HAI assays CCI [REDACTED])	All randomized participants in the immunogenicity subset who receive the study intervention and have at least 1 valid and determinate assay result (HAI assays CCI [REDACTED]) after vaccination.
Evaluable efficacy	All participants who are eligible, receive the study intervention to which they were randomized, and have no important protocol deviations, with surveillance starting at least 14 days after vaccination.
mITT efficacy	All randomized participants who receive the study intervention.

Population	Description
Safety	All participants who receive the study intervention.
Reactogenicity e-diary safety	All participants who receive the study intervention and have at least 1 day of e-diary data transferred for reactogenicity.

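### SAP 6.5.2.3 promises a count of vaccinated participants who transmit no e-diary, but names a population that excludes them, so total non-transmission can only be 0%

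*SAP*

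**What the plan says.** SAP 6.5.2.3 describes the e-diary compliance summaries. For each age group it commits to reporting "the number and percentage of vaccinated participants not transmitting the e-diary, transmitting the e-diary, and completing the e-diary for any day" in the reporting period, and then to a tabulation for each day and for all seven days. The section closes with a one-line paragraph that carries no exception: "The reactogenicity e-diary safety population will be used".

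SAP 4 defines that population as "All participants who receive the study intervention and have at least 1 day of e-diary data transferred for reactogenicity". Protocol 9.2 applies the same rule: participants must "have at least 1 day of e-diary transferred for reactogenicity". SAP 3.1.2 confirms the consequence, stating that a participant who reported no e-diary data is outside the reactogenicity population.

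SAP 3.4.2 defines the status to be counted: "If all data are missing for all items on the e-diary for all 7 days after vaccination, then the e-diary will be considered not transmitted". A completed e-diary, under the same section, needs all expected data on all seven days.

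SAP 5.3.1.1 drops participants with all seven days missing from the reactogenicity analysis, on the assumption that they are missing completely at random (MCAR). SAP 6.1.2.1 repeats the exclusion. SAP 6.5.2.1 separately plans a summary of participants excluded from each analysis population, with reasons, by study intervention and age group.

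**The concern.** The status to be counted and the population in which it is counted exclude each other. A participant who transmitted nothing has zero days of data, and the named population requires at least one.

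Local reactions and systemic events are primary safety endpoints, and their main analysis leaves out participants with no e-diary under an MCAR assumption. How many such participants there are, and whether the number differs between qIRV and QIV, is the first thing a reader would want to know about that exclusion. The compliance table is the natural place to look. As specified, it would print 0% in both groups regardless of the data, and its other percentages would rest on a denominator from which the complete non-responders had already been removed.

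**Working it through.** The plan states no compliance rate, so there is no figure of its own to reproduce. The check has two parts: a logical one that needs no assumption, and an arithmetic one that needs assumed rates.

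**1. Can a non-transmitter be in the table?**

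- Membership (SAP 4, Protocol 9.2): at least 1 of 7 days transferred.
- Not transmitted (SAP 3.4.2): 0 of 7 days with any data.

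Each day is either transmitted or not, which gives 2^7 = 128 patterns. Membership removes the single all-empty pattern and leaves 127. Of these 127, the number with 0 of 7 days is 0. Total non-transmission is therefore 0/N = 0% in every vaccine group and age group, and transmission on at least one day is 100%.

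The zero does not extend to single days. Among the 127 allowed patterns, 2^6 − 1 = 63 have Day 1 missing, so Day 1 non-transmission can be above 0 in this population. The same count applies to any other day.

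**2. What happens to the other percentages?**

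Let q be the share of vaccinated reactogenicity-subset participants with no day transferred, and c the share of all vaccinated subset participants who complete all seven days. Every completer belongs to the named population, so the numerator is unchanged while the denominator shrinks by a factor (1 − q):

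shown completion = c / (1 − q).

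The same factor applies to the daily transmission and completion percentages. The documents give neither q nor c. With c assumed to be 80%:

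| Assumed q | Calculation | Completion shown | Total non-transmission shown |
|---|---|---|---|
| 0% | 0.80/1.00 | 80.0% | 0% |
| 1% | 0.80/0.99 | 80.8% | 0% |
| 2% | 0.80/0.98 | 81.6% | 0% |
| 5% | 0.80/0.95 | 84.2% | 0% |
| 10% | 0.80/0.90 | 88.9% | 0% |

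For q between 1% and 10% and c between 70% and 85%, the overstatement runs from 0.7 points (0.70/0.99 − 0.70) to 9.4 points (0.85/0.90 − 0.85). It is zero if q is zero.

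**3. Comparison between groups (assumed rates only)**

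- Suppose 85% of transmitters complete in both groups, with q = 2% in one group and 8% in the other. Completion among all subset participants is 0.85 × 0.98 = 83.3% against 0.85 × 0.92 = 78.2%. The table shows 85% in both.
- Suppose instead that completion among all subset participants is 80% in both groups, with q = 4% and 8%. The table shows 0.80/0.96 = 83.3% against 0.80/0.92 = 87.0%.

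The distortion can thus hide a difference or create one. Neither case is a prediction for this trial.

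**The case against.** **The wider denominator may be what was meant.** The sentence that promises the count refers to vaccinated participants, and the population line is a separate paragraph placed after the daily tabulation. A programmer could apply the wider denominator to the first summary and the named population only to the daily one. That may well be the intention, but the closing line is unqualified and governs the section. If the wider denominator is meant, that line is wrong and needs correcting.

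**The information is planned elsewhere.** A reader might infer that the plan conceals non-response altogether. The documents do not support that. SAP 6.5.2.1 summarizes exclusions from every analysis population by group with reasons, and the reactogenicity e-diary safety population is one of those listed. A by-group count of participants without e-diary data may therefore appear there. Two limits remain. It does not correct the table in 6.5.2.3. And only a subset keeps a reactogenicity e-diary (Protocol 8.3.4, SAP 2.3), while the SAP does not say whether the exclusion reasons will separate subset members who transmitted nothing from participants never assigned a diary.

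**Complete non-response may be rare.** Protocol 8.10.1 requires sites to contact participants who are not completing the reactogenicity e-diary. This works against a large q, and the point about its unknown size stands. It does not make the count obtainable from the table.

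**The link to MCAR is indirect.** A reader might also infer that the plan relies on this table to support MCAR. Nothing in the SAP does so, and equal non-transmission in the two groups would not establish MCAR in any case. What remains is narrower: as written, the table cannot be used to examine the exclusion by group.

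**Conclusion.** The point holds as an internal contradiction with a limited, descriptive consequence. That total non-transmission can only be 0% follows from the definitions alone. The overstatement of transmission and completion by 1/(1 − q) is conditional on some subset participants transmitting nothing, and the 80.8% to 88.9% range rests on an assumed true completion of 80% and assumed q of 1% to 10%.

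A reader might go further and conclude that the reactogenicity results themselves are biased by this sentence. They are not. It concerns only compliance reporting, and the reaction-rate analyses in SAP 6.1.2 set their own population. No reactogenicity estimate, confidence interval, hypothesis test or efficacy result changes. What is affected is the accuracy of one compliance summary and the ability to examine the SAP 5.3.1.1 exclusion by vaccine group. It should be corrected because the stated rule cannot deliver the statistic that the section promises.

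**What to change.** Replace the last sentence of SAP 6.5.2.3 with one to this effect: *The denominator for all e-diary transmission and completion summaries is all vaccinated participants assigned to the reactogenicity subset, by vaccine group and age group.* The whole safety population would not serve, because it includes participants who were never given a reactogenicity e-diary. Keep the reactogenicity e-diary safety population for the reaction-rate tables in SAP 6.1.2.

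The cost is one sentence and the denominator of one descriptive table. Reported compliance may look slightly less favourable.
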